QLQ-BR23	Quality of Life Questionnaire Breast Cancer Module
QLQ-C30	Quality of Life Questionnaire Core 30
RECIST	Response Evaluation Criteria in Solid Tumors
SAE	serious adverse event
SAF	Safety
SAP	Statistical Analysis Plan
SD	stable disease
SOC	System Organ Class
TLR	Top Line Results
TSAP	Translational Statistical Analysis Plan
U/S	Ultrasound
WT	Wild type

1. Introduction

This Statistical Analysis Plan (SAP) is based on the Clinical Study Protocol for the ABCSCG study 38 (external study code: GO28888/BIG-3-13/SOLTI 1205) in its third amended version from July 27, 2015) and provides a detailed description of all statistical analyses planned to be conducted within this trial at predefined timepoints.

All analyses described herein are performed in accordance to the guidelines of the International Conference on Harmonisation of Technical Requirements for Registration of Pharmaceuticals for Human Use (ICH).

2. Study details

2.1. Study objectives

2.1.1. Primary objective

The primary objective of this study is to evaluate the efficacy of letrozole plus GDC-0032 versus letrozole plus placebo in women with ER+/HER2- early stage breast cancer, as measured by the following co-primary objectives:

- Tumor overall objective response rate (ORR) by centrally assessed breast magnetic resonance imaging (MRI) via modified Response Evaluation Criteria in Solid Tumors (RECIST) 1.1 ([Appendix 1](#)~~Appendix 4~~) in all enrolled patients and PIK3CA mutant (MT) patients
- pCR rate in breast and axilla (ypT0/Tis, ypN0 as defined in the American Joint Committee on Cancer (AJCC) staging system) by local evaluation in all enrolled patients and PIK3CA MT patients

Information on PIK3CA mutation status is assessed centrally.

2.1.2. Secondary objectives

The secondary efficacy objectives of this study are the following:

- Tumor overall ORR, assessed by centrally assessed breast MRI via modified RECIST 1.1 in PIK3CA wild type (WT) patients
- pCR rate in breast and axilla (total pCR ypT0/Tis ypN0) by local evaluation in PIK3CA WT patients

The following secondary objectives will be performed in all enrolled patients and separated by PIK3CA mutation status:

- Compare letrozole plus GDC-0032 with letrozole plus placebo in terms of locally assessed ORR as measured by modified RECIST 1.1 criteria using the following methods:
 - o Breast ultrasound
 - o Clinical breast exam (i.e., palpation)
 - o Mammography
- Central assessment of changes in Ki67 levels upon treatment with letrozole plus GDC-0032 versus letrozole plus placebo from baseline to Week 3; baseline to surgery; and Week 3 to surgery
- Compare the centrally derived, preoperative endocrine prognostic index (PEPI) score upon treatment with letrozole plus GDC-0032 versus letrozole plus placebo.
- Evaluate the changes in enhancing tumor volume from baseline to surgery as measured by breast MRI via central assessment.
- Evaluate different definitions of pCR including the following: a) ypT0, ypN0, and b) ypT0/is, ypNX (breast pCR).

2.1.3. Safety objectives

The safety objective for this study is to evaluate the safety of letrozole plus GDC-0032 versus letrozole plus placebo.

The safety and tolerability of GDC-0032 will be assessed using the following safety outcome measures:

- Incidence, nature, and severity of adverse events (AEs) graded according to National Cancer Institute Common Terminology Criteria for AEs (NCI CTCAE), v4.0
- Incidence and type of AEs leading to dose discontinuation, modification, or delay
- Serious adverse events (SAEs)
- Protocol-defined AEs of special interest (AESI)
- Clinically significant changes in vital signs and in clinical laboratory results during the AE reporting period

2.1.4. Patient-reported outcome objectives

The patient-reported outcome (PRO) objectives for this study are as follows:

- Evaluate and compare PROs of treatment-related symptoms, patient functioning, and health-related quality of life (HRQoL), including side-effects of therapy (e.g., sore mouth/tongue, difficulty swallowing, diarrhea, skin problems), between treatment arms as measured by the European Organisation for Research and Treatment of Cancer (EORTC) Quality of Life Questionnaire Core 30 (QLQ-C30) and the modified Breast Cancer Module (QLQ-BR23)

2.1.5. Exploratory objectives

The exploratory objectives for this study are as follows:

- ORR, pCR rate, and PEPI scores according to the decrease in Ki67 after 2 weeks of letrozole plus GDC-0032 and letrozole plus placebo.
- To evaluate changes in tumor cellular composition as assessed by diffusion-weighted MRI
- To assess whether biomarkers from tumor tissue or blood, including but not limited to somatic cancer associated mutations, phosphatase tensin homolog (PTEN) expression, pro-survival pathways (such as phosphatidylinositol-3-kinase (PI3K)/AKT, mitogen-activated protein kinase (MAPK) etc.), apoptotic markers, hormone receptor expression levels, and levels of RNA and DNA expression are predictive of response
- To determine whether inhibition of PI3K with GDC-0032 results in changes in downstream markers in tumor tissue and to examine the relationship to anti-tumor activity
- To assess concordance and percentage of PIK3CA mutation status from baseline biopsy and surgical specimen
- To assess emergence of resistance alleles from tumor tissue or blood

- To assess concordance of the different imaging modalities (MRI [volume, enhancement, diffusion metrics], ultrasound, mammography) in measuring tumor response
- To assess the pharmacokinetics and possible drug interaction between letrozole and GDC-0032 upon concomitant administration
- To assess the correlation of GDC-0032 drug levels and GDC-0032 related response (efficacy or AEs [e.g., colitis, rash])
- To assess the influence of pharmacogenetic polymorphisms on GDC-0032 and/or letrozole on pharmacokinetics (e.g. drug metabolizing enzymes and transporters) and response (either efficacy and/or AEs)
- Compare the rates of breast-conserving surgery (BCS) and conversion to BCS in letrozole plus GDC-0032 versus letrozole plus placebo

2.2. Study design

This is a two-arm, randomized, double-blind, multicenter, pre-operative study to evaluate the effect of combining letrozole and GDC-0032 versus letrozole and placebo in postmenopausal women with estrogen receptor positive (ER+) / human epidermal growth factor receptor 2 negative (HER2-) untreated, Stage I-III operable breast cancer whose primary tumors are ≥ 2 cm. Patients with cT4 or cN3 tumors are not eligible. Standard of care assessments/procedures (e.g., bilateral mammogram) performed within 28 days of Day 1 dosing do not need to be repeated for screening purposes. After confirmation of all the eligibility criteria, patients will be randomized to one of the two treatment arms. The study will enroll approximately 330 patients at approximately 110 global sites.

[figure not shown]
At Weeks 1, 5, 9, 13, and 16 the primary breast tumor and axillary lymph nodes will be assessed by clinical breast examination (palpation and caliper measurement). Suspicion of progression based on clinical exam at any time should be further evaluated. In addition to the safety assessments conducted at the scheduled follow-up visits, patients will be contacted by telephone for a general assessment of adverse events at Weeks 7 and 11.

At Week 9, a breast ultrasound will be performed to ensure that there is no progressive disease (PD) and for the purpose of surgery planning. Suspicion of PD on breast ultrasound should be confirmed by investigator-assessed breast MRI. Patients with primary disease not evaluable (NE) by ultrasound at baseline should be assessed by MRI at Week 9. Suspected progression in nodes should also be confirmed by fine needle aspiration (FNA) if these nodes had not been previously shown to be cytologically positive for cancer. Patients with PD (as defined by modified RECIST 1.1, [Appendix 1](#)~~Appendix 1~~), can either proceed directly to surgery or be taken off of the study, according to the investigator's decision. If the patient goes off-study, every reasonable effort should be made to obtain a new biopsy prior to beginning another systemic treatment.

During Week 16, breast MRI will be done for the purpose of primary endpoint analysis. Clinical breast exam, breast ultrasound, and mammography will also be conducted prior to surgery for the purpose of the secondary endpoint analysis.

Blood samples for exploratory endpoint analysis will be collected on Day 1 prior to dosing, at Week 9, and prior to surgery (Week 16 visit) and at the 4-weeks postsurgical follow-up visit.

Figure 1 Study Schema

	Pretreatment	Day 15 (Week 3)	Week 9	Week 16	Surgery (Week 17-18)
Tumor tissue	●	●			●
MRI	●		●	●	
Breast U/S	●		●	●	
Mammogram	●			●	

BC=breast cancer; ER+=estrogen receptor positive; MRI=magnetic resonance imaging; QD=once daily; U/S=ultrasound.

Suspicion of PD on breast ultrasound should be confirmed by investigator-assessed breast MRI. Patients with primary disease not evaluable (NE) by ultrasound at baseline should be assessed by MRI at Week 9.

2.2.1. Surgery

Surgery will take place after at least 16 weeks of treatment, during Weeks 17 – 18. Surgery should be performed within 4 days after the last dose of GDC-0032, if possible, to best observe pharmacodynamic knockdown with GDC-0032 in the surgical specimen. Surgery may be delayed due to toxicity or other safety issues. A maximum of 16 weeks of GDC-0032 can be administered. Letrozole can be continued up to surgery by investigators decision. Information on the type of surgery will be collected and recorded. Surgery specimens will be collected for histological examination to assess for pathologic complete response (pCR) and

for other endpoint analyses. The co-primary efficacy endpoint of the primary objective, i.e. pCR (ypT0/is, ypN0), will be established via a local review following completion of neoadjuvant therapy and surgery.

An Independent Review Facility (IRF) will be used to determine the tumor ORR via MRI. IRF procedures are detailed in the IRF charter.

A post-surgery visit will be performed 4 weeks (+ 1 week) after surgery, and will mark the end of the study. Assessment of AEs and general safety will be collected at this visit.

2.2.2. Study duration – end of study

The end of study (EOS) is defined as the date when the last patient has her post-surgery visit. The total duration of the study is expected to be approximately 24 months for enrollment, plus 5.5 months after last patient in.

2.3. **Randomization and stratification criteria**

After written informed consent form (ICF) has been obtained and eligibility has been established, the study site will obtain a patient's identification number and treatment assignment using a permuted block randomization algorithm via an interactive voice or web-based response system (IxRS).

Patients will be randomized into one of the two treatment arms in a 1:1 ratio based on the following stratification factors:

- Tumor Size (T1-T2 vs. T3)
- Nodal Status (cytologically positive vs. radiologically or cytologically negative). If on ultrasound examination there is evidence of suspicious axillary lymph nodes at the baseline examination, then FNA or core biopsy is required to confirm nodal status.

2.3.1. Blinding

Investigators and patients will be blinded to treatment assignment of GDC-0032 or placebo.

For emergency situations, the investigator will be able to break the treatment code by contacting the IxRS. The responsibility to break the treatment code in emergency situations resides solely with the investigator. For non-emergency situations, the investigator needs to obtain approval from the Medical Monitor to break the treatment code. Unblinding during the study will result in the withdrawal of a patient from the study. For regulatory reporting purposes, and if required by local health authorities, the Sponsor will break the treatment code for all serious, unexpected or suspected adverse reactions that are considered by the investigator or Sponsor to be related to study drug.

While PK samples must be collected from patients assigned to the comparator arm to maintain the blinding of treatment assignment, PK assay results for these patients are generally not needed for the safe conduct or proper interpretation of this trial. The PK assay group will be unblinded to patients' treatment assignments to identify appropriate PK samples to be analyzed and bioanalytical methodology to employ. However, the PK scientist does not have access to the PK assay results and therefore stays blinded until the PK assay results need to be interpreted and reported. Samples from patients assigned to the comparator arm will be analyzed for letrozole. However, GDC-0032 assay will be analyzed by request (i.e., to evaluate a possible error in dosing).

2.4. Number of subjects - sample size estimation

This study is designed for testing the effect of GDC-0032 on the two co-primary endpoints in all enrolled patients and in the PIK3CA MT patients and plans to enroll 330 patients in total. Assuming the PIK3CA mutation status will not be available (unknown) for approximately 10% of the patients and the prevalence of PIK3CA MT is 40%, there will be approximately 120 patients in the PIK3CA MT cohort.

Given that the PIK3CA mutation status is not a stratification factor for randomization, there might be a possible imbalance between treatment arms within the PIK3CA MT cohort, which may reduce the statistical power in this cohort. To ensure the study provides sufficient statistical power even when the treatment assignment is imbalanced, the sample size was calculated based on a conservative scenario by assuming that the treatment assignment imbalance in PIK3CA MT is 40% vs. 60%. The sample size was calculated based on a χ^2 -test using continuity correction (Ury and Fleiss 1980).

To control an overall, two-sided, family-wise error rate under 20% for each analysis population, we use a two-sided significance level of 16% and 4% for the co-primary endpoints MRI ORR, and pCR, respectively.

Assuming 10% of the patients are unevaluable for the MRI ORR, approximately 300 enrolled patients and 108 patients in the PIK3CA MT cohort will be evaluable for analyses. This sample size allows us to detect an absolute percentage increase of 24% in MRI ORR rate in the letrozole plus GDC-0032 arm (64%) versus the letrozole plus placebo arm (40%; Smith et al. 2005; Ellis and Ma 2007) in the PIK3CA MT cohort at 80% power and 16% two-sided significance level. The minimal detectable difference for ORR is approximately 15%.

Assuming that all patients are evaluable for pCR (i.e., approximately 330 enrolled patients and 120 in the PIK3CA MT cohort), this sample size provides 80% power to detect an absolute percentage increase of 18% in pCR in the letrozole plus GDC-0032 arm (19%) versus the letrozole-only arm (1%, Smith et al. 2005; Ellis and Ma 2007) in the PIK3CA MT cohort at the 4% two-sided significance level. The minimal detectable difference for pCR rate is approximately 13%.

The study is considered positive if at least one population shows a statistically significant result regarding the co-primary endpoints.

If the prevalence of the *PIK3CA* mutation is lower than assumed, if there is more substantial treatment assignment imbalance in the *PIK3CA* MT cohort than assumed, or there is an increased number of unevaluable patients for the MRI ORR, the sample size may be increased to obtain the level of power at 80%, and the enrollment may be limited to patients with *PIK3CA* MT.

3. Statistical methods

3.1. Data handling conventions

3.1.1. Data entry errors and potential outliers

Patients may have potential outliers for particular observations. Observations will be checked for correctness by the study team before data freeze and at the time point of data freeze all data should be correct. Remaining potential outliers based on correct values will be included in analysis. If assumptions or data structure do not allow planned analyses, analyses will be updated appropriately. However, sensitivity analyses excluding these measurements may be calculated to evaluate the influence of such extreme values. Values found to be incorrect due to data entry error after database closure will be excluded from all analyses as missing values. Incidence of incorrect values and potential outliers will be listed and summarized by treatment arm.

3.1.2. Missing data

Subjects may have missing specific data points for a variety of causes. In general, data may be missing due to a missed visit, non-evaluability of a specific clinical measurement at its planned clinical visit or a subject's early withdrawal from study. The general procedures outlined below describe what will be done when a data point is missing.

3.1.2.1. *Imputations of missing data*

Generally, only evaluable measurements are considered for the analyses. No values are imputed for missed or non-evaluable visits. In case of primary and secondary efficacy endpoints possible specific requirements are stated in the according analysis sections.

3.1.2.2. *Partial dates*

Partially incomplete dates (day or day/month missing) will be imputed for dates related to AEs, to concomitant medication and medical history. Completely missing dates and missing years will not be imputed.

For DOB imputed dates will be used to derive the age of the patients since only month and year are captured due to regulatory reasons in some participating countries. DOB must not

have missing month information and hence, missing months will not be imputed. DOB will be imputed as described in the following table:

	Missing	Impute	Exception
DOB	Day	15	--

Dates belonging to AEs and concomitant medication will be imputed as described in the following table:

	Missing	Impute	Exception
Start date	Day	01	Date of first dose of study drug if imputed date would be prior to date of first dose of study drug
	Day/Month	01JAN	Date of first dose of study drug if imputed date would be prior to date of first dose of study drug
Stop date	Day	Last day of the month	Patient EOS date if the imputed date would be after patient EOS date
	Day/Month	31DEC	

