3.1.4. Derived endpoints

EOS visit: The date of end of study visit of each patient is defined as the maximum date of all dates during the post-surgery visit for patients who ended the study per protocol and it is the date of early EOS for patients who ended the study due to other reasons. Early EOS occurs

when a patient does not undergo surgery and/or post-surgery visit (independent of the treatment visits).

Early end of treatment (EOT): Early discontinuation from treatment occurs when a patient does not take more than 90% of investigational product (IP; =14.5 weeks=72days of dosing).

Age: Age will be calculated as the time from imputed DOB to date of randomization based on eCRF information.

PEPI score: The PEPI score will be calculated (for relapse-free survival and breast cancer-specific survival) on the basis of pathological tumor size (locally assessed – as ypTStage), node status (locally assessed – as ypNStage), Ki67 level (centrally assessed - VHIO: variable Ki67ResN), and ER status (centrally assessed - VHIO: variable ERResN, Allred score) according to Ellis et al (2008).

Tumor overall ORR assessed by modified RECIST 1.1 criteria:

Lesions should be evaluated and documented at all assessments (even if they have disappeared – laterality and location for the lesion will be set to ‘not available’). Documentation should be done at all subsequent visits for the modality where it was detected. For each modality, subject response is always relative to screening (baseline assessment) of that modality. Subject overall response per modified RECIST 1.1 criteria is assessed only at Week 16. Assessments of disease at visits prior to Week 16 visit are to rule out progression.

Target and non-target lesions are identified at screening, while new lesions are only identified after screening. If a new finding is equivocal on a particular modality, and not deemed suspicious enough to warrant clinical follow-up it should not be documented as a new lesion on that modality. Lymph nodes may be identified as non-target lesions at screening or as new lesions at another visit. Lymph nodes are not expected to disappear; a complete response (CR) may be documented if the lymph node becomes completely non-pathologic in appearance (~equivalent to non-lymph node lesion disappearing).

If a target lesion was present at screening the response at Week 16 should be documented as given in Table 1 in [Appendix 1](#) ~~Appendix 1~~.

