3.5.2. Baseline demographic and disease characteristics

Demographic variables, stratification factors and other baseline characteristics will be summarized descriptively by treatment arm. The demographic variables age (metric), gender (female, male), ethnicity (Hispanic/Latino, not Hispanic/Latino) and race (American Indian/Alaska Native, Asian, Black/African American, Native Hawaiian/Other Pacific Islander, White) will be reported. Tumor size (T1-T2, T3) and nodal status (cytologically positive, radiologically or cytologically negative) are the two observed stratification factors by IxRS. Additionally, the tumor specific variables tumor stages (N-Stage; M-Stage) and tumor grading, and hormone receptor statuses (ER and progesterone receptor (PgR)), Ki67, ER status (Allred score), PEPI score as well as the Eastern Cooperative Oncology Group (ECOG) status will be analyzed.

Frequencies and percentages, means and standard deviations or medians and interquartile ranges will be given depending on the scale of the variable. Important protocol deviations

IPDs include inclusion and exclusion criteria, as well as selected variables belonging to additional relevant screening assessments, study treatment administration/dispensation, concomitant medication, primary endpoint, study treatment/randomization, study procedures/assessments, withdrawal/termination criteria and safety reporting. The IPDs are defined in a separate document listing all IPDs, their classification and additional details. IPDs will be summarized in total and by treatment arm and will be listed by study site, treatment arm and patient number.

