3.7.2. Analysis for secondary endpoints

The two secondary efficacy endpoint measures in PIK3CA WT population will be summarized by treatment arm and will be analyzed analogous to the primary efficacy endpoints. Information on PIK3CA mutation status (HistoGeneX: variable PIK3CAREsC) is assessed centrally. Patients with early study termination and hence missing efficacy outcome, as well as patients who are NE for MRI by central review will be considered as non-responders in the analysis.

The further endpoint measures will be summarized by treatment arm and will be compared between the two treatment arms within each population based on appropriate statistical analyses: locally assessed ORR will be compared using a Cochran Mantel-Haenszel test, stratified by tumor size and nodal status within each method; change in Ki67, PEPI score and change in enhancing tumor volume will be compared by appropriate regression analysis models (depending on the distribution of the variables), e.g. logistic regression models, adjusted for tumor size and nodal status. For each of the different definitions of pCR, comparisons between treatment arms will be done by Cochran Mantel-Haenszel test, stratified by tumor size and nodal status.

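### The SAP has no rule for surgical Ki67 and PEPI after a pCR; its evaluable-only default would tend to lose these patients, mostly from the GDC-0032 arm if pCR differs as planned

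*SAP*

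**What the plan says.** **General rule (SAP 3.1.2).** "Generally, only evaluable measurements are considered for the analyses", and "No values are imputed for missed or non-evaluable visits". The section leaves room for exceptions: "In case of primary and secondary efficacy endpoints possible specific requirements are stated in the according analysis sections".

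**Where an exception would stand (SAP 3.7.2).** The only handling rule there is in the paragraph on the two PIK3CA wild-type endpoints, MRI response and pCR. Patients who leave early without an outcome count as non-responders, and "patients who are NE for MRI by central review will be considered as non-responders in the analysis". The next paragraph says of the other endpoints only that "change in Ki67, PEPI score and change in enhancing tumor volume will be compared by appropriate regression analysis models", adjusted for tumour size and nodal status.

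**How PEPI is built (SAP 3.1.4).** "The PEPI score will be calculated (for relapse-free survival and breast cancer-specific survival) on the basis of pathological tumor size", together with nodal status, central Ki67 and central ER, following a cited publication. The SAP does not write out how a pCR is scored. Section 3.7.1 places PEPI at surgery, and two of its three Ki67 intervals end at surgery.

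**Baseline table (SAP 3.5.2).** PEPI is also among the baseline characteristics: "PEPI score as well as the Eastern Cooperative Oncology Group (ECOG) status will be analyzed".

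**The concern.** Ki67 and ER at surgery need tumour tissue. A patient with no invasive tumour left generally has nothing on which to score them. Under the evaluable-only default, her Ki67 change to surgery is missing. Her PEPI is missing too if all four components are required. The value is then absent because treatment worked, and adjusting for tumour size and nodal status does not correct for that.

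If pCR is more frequent on GDC-0032, the analysis compares residual tumours only and leans against the arm with more complete responses. This also sits badly with section 3.3.1, under which secondary analyses include all randomized patients. The primary endpoints have an explicit rule for missing outcomes in 3.6.2; these two secondary endpoints have none.

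The baseline listing of PEPI is a separate, smaller inconsistency. A score built from post-treatment pathological stage cannot be a baseline characteristic.

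**Working it through.** **Inputs from SAP 2.4:** pCR 19% (GDC-0032) vs 1% (control) in the mutant cohort; two-sided alpha 4%; power 80%; 40:60 allocation; continuity correction; 120 mutant patients and 330 in all.

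**Inputs assumed:** every pCR patient lacks a surgical Ki67 (an upper limit). The share q of lowest-risk PEPI among patients without pCR is the same in both arms, from 10% to 30%. Alternative pCR rates are 5% vs 1% and 2% vs 1%. The SAP gives no figure for any of these, and no expected pCR rate for all enrolled patients.

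**Step 1: reproduce the SAP's figure.** Let r = 1.5 GDC-0032 patients per control and d = 0.18. The pooled rate is (0.01 + 1.5 × 0.19)/2.5 = 0.118. The uncorrected control-arm size is

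n' = [2.054 × √(2.5 × 0.118 × 0.882) + 0.842 × √(1.5 × 0.01 × 0.99 + 0.19 × 0.81)]² / (1.5 × 0.18²) ≈ 40.

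With the continuity correction, n = (n'/4) × [1 + √(1 + 2(r + 1)/(n' r d))]² ≈ 49, so the total is 49 × 2.5 = 122.5 against 120 stated. Corrected power at 48 control and 72 GDC-0032 patients is 79.1% against 80%. The figure is reproduced, so 19% vs 1% is the SAP's working assumption. The SAP has no planning figure for Ki67 or PEPI.

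**Step 2: patients lost = arm size × pCR rate.**

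| Setting | GDC-0032 lost | Control lost |
|---|---|---|
| Mutant, 60 per arm, 19% vs 1% | 60 × 0.19 = 11.4 | 60 × 0.01 = 0.6 |
| Mutant, 72 and 48, 19% vs 1% | 72 × 0.19 = 13.7 | 48 × 0.01 = 0.5 |
| All, 165 per arm, 5% vs 1% | 165 × 0.05 = 8.3 | 165 × 0.01 = 1.7 |
| All, 165 per arm, 2% vs 1% | 165 × 0.02 = 3.3 | 165 × 0.01 = 1.7 |

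In the first row, 11.4/12.0 = 95% of the losses fall in the GDC-0032 arm, leaving 48.6 and 59.4 patients.

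**Step 3: effect on PEPI.** Among evaluable patients the lowest-risk share is q in both arms, so the reported difference is 0. With pCR counted as lowest risk, the share is pCR + (1 − pCR) × q, and the difference between arms is (pCR difference) × (1 − q).

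| q | 19% vs 1% | 5% vs 1% | 2% vs 1% |
|---|---|---|---|
| 10% | 27.1% − 10.9% = 16.2 points | 4 × 0.9 = 3.6 points | 1 × 0.9 = 0.9 points |
| 20% | 35.2% − 20.8% = 14.4 points | 4 × 0.8 = 3.2 points | 1 × 0.8 = 0.8 points |
| 30% | 43.3% − 30.7% = 12.6 points | 4 × 0.7 = 2.8 points | 1 × 0.7 = 0.7 points |

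No size can be given for Ki67 change to surgery, because the SAP states no Ki67 distribution. The losses in step 2 apply to it equally.

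**The case against.** - **Exclusion is inferred.** A reader might conclude that the plan excludes patients with pCR. It does not say so. PEPI scoring is delegated to a publication that is not at hand and may cover a pCR, and ypT and ypN are known in these patients. Placing such a patient in a category from her stage could be read as scoring and not as the imputation that 3.1.2 rules out. This stands, and it makes the PEPI part conditional. It does not help Ki67 change, for which no derivation is cited.
- **A pCR need not mean no tumour.** The definition in 2.1.1 allows residual in situ disease, and the SAP does not say whether Ki67 or ER is scored on it. This stands; the losses in the working are upper limits.
- **The largest figure is the powering alternative rescaled.** A reader might take 13 to 16 points as the expected bias in the whole trial. The documents do not support that. The 19% vs 1% belongs to the mutant cohort, and the result is 18 points times (1 − q) under an assumed equal q. At small pCR differences the effect is negligible.
- **The pCR benefit stays visible.** pCR is a co-primary endpoint, and 3.7.1 adds two further definitions. This stands: only PEPI and the Ki67 intervals ending at surgery are exposed.
- **The unexpected results.** Section 5 mentions unexpected Ki67 and PEPI results. A reader might infer that pCR-related missingness explains them. Nothing in the SAP shows this; the addendum looks only at time from end of treatment to surgery.

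The gap remains: 3.1.2 points to the analysis sections for exceptions, and 3.7.2 has none for these endpoints.

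**Conclusion.** The concern holds in conditional form and deserves correction. Followed as written, the SAP would tend to drop patients with no residual invasive tumour from the PEPI and Ki67-to-surgery comparisons, unless the cited PEPI publication provides for them. The bias runs against GDC-0032 if pCR is more frequent in that arm. Its size depends mainly on the pCR difference: 13 to 16 PEPI points at the mutant-cohort planning rates, about 3 points at 5% vs 1%, and under 1 point at 2% vs 1%. These figures assume that every pCR patient lacks a surgical Ki67, that a pCR belongs in the lowest risk category, and that q is equal across arms. Confidence is medium. The baseline listing of PEPI contradicts 3.1.4 and 3.7.1 and needs no assumption, but it is minor.

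**What to change.** 1. **PEPI (3.1.4 and 3.7.2).** State that patients with pCR and no evaluable surgical Ki67 or ER are included in the lowest risk category, with the evaluable-only analysis as sensitivity. Check the cited publication first; if it has a rule for them, write that rule out.
2. **Ki67 change to surgery (3.7.2).** Keep the adjusted regression and add a sensitivity analysis that gives these patients the best rank. Replacing the regression outright would be a debatable change of estimand.
3. **Reporting.** Tabulate missing surgical Ki67 and PEPI by arm and reason, with pCR as its own reason. State whether Ki67 and ER are scored on residual in situ tumour.
4. **Baseline (3.5.2).** Remove PEPI from the baseline summary.
5. **Timing.** Label the change as post hoc if it is made after unblinding. Section 5 shows that Ki67 and PEPI results had already been seen when the addendum was written.

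The cost is a few sentences or an addendum entry; the components are already collected. The downside is one assigned category, which these documents do not themselves justify, and one extra sensitivity analysis for Ki67.
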